Study Protocol

The Assessment and management of Obesity
and Self-maintenance (AMOS) Clinic:
Implementation and Evaluation of the AMOS
Model of Care

Version 7

[figure not shown]

Table of Contents

Title	2
Summary	2
Researchers/Investigators	2
Rationale and Background	3
Study Goals and Objectives	5
Aim.....	5
Objectives.....	5
Outcomes	5
Study Design	7
Rationale for Study Design	8
Methodology	8
Randomisation.....	8
Study Intervention.....	9
Clarification of Intervention.....	9
Usual Care Contextualised to the Rural Setting.....	11
Management of Cross Contamination.....	12
Orlistat and other Weight Medications.....	12
Orlistat as the Pharmaceutical Intervention & Bariatric Surgery.....	13
Flow Chart.....	14
Study Duration/Timelines	15
Study Population	15
Participants Inclusion/Exclusion Criteria	15
Lay Description of Participation.....	15
Nature of Existing Relationships and Voluntary Consent.....	16
Impact of Research on Participant/Researcher Relationship.....	16
Male to Female Ratio.....	16
Consideration for Vulnerable Groups.....	16
Data Management and Statistical Analysis	16
Data Management.....	16
Statistical Analysis.....	17
Justification of Effect Size.....	18
Expected Outcomes of the Study	21
Informed Consent	21
Advertisement of Study.....	21
Exposure of Person to Disadvantage or Risk.....	22
Seeking Consent.....	22
Confidentiality and Privacy.....	22
Safety Considerations	23
Expected Benefits to the Wider Community.....	23
Expected Benefits to Participants.....	23
Risk of Harm.....	23
Mechanisms to Monitor the Project.....	24
Data and Safety Monitoring.....	24
Resources	24
Other Personnel Relevant to Research Project.....	24
Training.....	25
Project Funding.....	25
Project Management	26
Prior Reviews	31
Dissemination of Results and Publication	31
References	32

Study Protocol

Title

The Assessment and Management of Obesity and Self-Maintenance (AMOS) Clinic: Implementation and Evaluation of the AMOS Model of Care

Summary

The aim of this project is to assess the effectiveness of an integrated model of obesity care for adult patients with diabetes who also have obesity. The research design is a randomised controlled clinical trial. The project will recruit 212 patients with diabetes and randomise them to active intervention or usual care. The active intervention group will receive an integrated, multidisciplinary model of care for obesity management.

Researchers/Investigators

Principal Investigators

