
TSRAC QUESTION 8 (Response)
 
 Initially the decision was made to use the K10 as a brief measure of psychological distress. This was intended to act as a “triage” for psychological support grouping. Initially the discussions agreed that this was the best option in terms of being conservative in the amount of time being requested of participants. However, the K10 is more a population measure (with norms) rather than used to compare specific research populations. The DASS scale is not being utilised within this research study The PHQ-9 (depression) and GAD-7 (Anxiety) have been chosen as they are validated tools widely used in other research that has focused on the issues of diabetes or obesity, such as the MILES study. The PHQ and GAD are based on the DSM-IV diagnostic criteria. The SF-36 is a generic measure of quality of life. There are a number of other options, however many of them are diabetes specific (or focus on another specific health condition). Given the AMOS project is potentially going to be rolled out to those without diabetes, a more generic measure is more appropriate. It is widely used, acceptable reliability and validity, and norms are available for a range of clinical and nonclinical populations. Time points for assessment and review have been chosen due to fluctuating nature of these measurements and as used in other peer reviewed literature 							
Health professional referral measures							
Referral to other health professionals	X		X		X		
Psychology review	X		X		X		
Physiotherapy review*	X		X		X		
Dietitian review #	X		X		X		
Group training (Stanford – GTMOL)	X		X		X		

 Referral points to AHPs and group program were chosen as outcome measures as a variable that has altered care or treatment Time points for this collection was selected due to presumed referral in line with study protocol. 							

Study Design TSRAC v2 Q1

- Parallel randomised waitlist control trial conducted in the Diabetes Centre of the THO-North West; individuals wait listed for the obesity clinic (*the experimental intervention*) becomes the control group.
- Participants who fit the inclusion criteria will be recruited from pre-existing clinics and listed in order of BMI – subsequently randomly assigned to the two arms of the study via use of an Excel Random Number Generator.

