- Recruitment will start initially with the first 106 identified through the excel program for the two groups and will continue until 106 participants have been recruited into both arms.

Rationale for Study Design TSRAC QUESTION 1 (Response)

- According to the NHMRC levels of evidence, a RCT is level 2 evidence and a systematic review of RCTs is level 1 evidence. Program evaluation is not a research method. Rather, program evaluation is conducted using a range of different research methods that are adapted to the task of evaluation depending on the program and the circumstances of its implementation. As this study is an intervention study that examines the effectiveness of an obesity model of care in patients with type 2 diabetes, the higher level of evidence is a RCT and is the study design that the research team wishes to use.
- Initially, all patients will be provided with quality evidenced based care at all times for diabetes and obesity; this form of care for both groups will not alter.
- The potential difficulty for team members to provide services differently depending on whether a client is in the control or intervention group has been addressed by separating participants from the control and intervention group into different clinics. The control group will be seen in the usual diabetes clinic with no particular focus on obesity management and/or the many factors that impact on obesity.
- At differing times a patient in the control group may have an assessment taken ie DASS due to an issue isolated in the course of the clinic however; this is not common but will be accounted for post-hoc in our data analysis.
- The intervention group will have onsite on the day of the clinic a more extensive multidisciplinary team that will be involved in assessment and treatment; unlike the control group clinic.
- Services and treatment will differ due to these assessments and measurement of other markers eg psychometric and pain scales that will prompt differing care and treatment plans.

Methodology

TSRAC QUESTION 2 and 3 (Response)

Randomisation

- All patients referred to the Diabetes Centre are listed in the services clinical software program DiaBASE.
- The list of potential participants was drawn from this program (that is inclusive of all patients as at 10/9/2014)

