- Following 3 months of lifestyle modification and intensive therapy if weight loss <5% Olistat will be introduced
- At 6 months participants will be referred to self-management program for ongoing behaviour modification
- For relevant cases at 12 months if weight loss not <5% and pathology demonstrates ketosis referral for surgical review
- Bariatric surgical assessment and patient counselling will be provided to determine:
 - whether surgery is indicated;
 - the patient's desire for, and likely tolerance to surgery; and
 - if so, what surgery type is most appropriate for the patient (Nguyen, 2013).

Following the completion of the up to 24 month program (the intervention) participants (both intervention and control) will be invited to continue to be part of the research project by way of providing follow-up data to determine sustainability of the intervention and project. Given Participants are existing patients of the service and will continue to be review as part of routine care at the Diabetes Centre, at their 24 month collection point (intervention and control) participants will be invited to continue with a collection of indicated markers at 6 and 12 months post intervention. If at their last visit (24 months) the participant indicates that they are happy for this to occur this verbal consent will be recorded on the spreadsheet used to collect project data – ie consent given: yes and date. If consent is provided by the participant, ongoing data will be collected following intervention period at 6 and 12 months post intervention.

Intervention Clarified/Differences in two arms of Study TSRAC QUESTION 12 (Response)

- Intervention of interest – **individualised** multidisciplinary multi-intervention assessment and treatment
- The impact of a model of care that assesses, triages and treats **all** factors impacting on metabolic processes from point of entry

Differences in two arms	
Control Group	Intervention Group

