- “The Australian Clinical Practice Guidelines for the Management of Overweight and Obesity in Adults” (NHMRC, 2013) provide an evidence-based, stepped approach to obesity management. The first level of management is lifestyle intervention, comprising exercise, nutrition and psychological intervention. The second level of management is medication management. The third level of management is surgery. The guidelines consider that higher levels of management are indicated when lower levels of management have been insufficient to achieve desired clinical outcomes. This is the management approach the hospital research team will adopt in their patient management strategies.
- However, the control group in this study will receive ‘usual care’. The research team is aware this means patients in the intervention or control groups may receive lifestyle, medication and / or surgical management through alternative clinical pathways (e.g. through primary care, private hospital or other sources of clinical support). This is usual in obesity clinical trials with a ‘usual care’ control arm (see the Australian Clinical Guidelines discussion on this). Consistent with other obesity studies, we will account for any differences post-hoc in our data analysis.

AMOS Research Project Participant Flow Chart

Study Duration/Timelines:

Stage 1: Recruitment of participants to study and informed consent (0 – 3 months)

Stage 2: Data collection, referral to therapies (3 – 12 months)

Stage 3: Ongoing recruitment and informed consent (6 – 9 month)

Stage 4: Initial data analysis (15 months)

Stage 5: Data Analysis and Interpretation (24-26 month)

Stage 6: Presentation and publication (15 and 26 month)

Study Population

Participants

Inclusion Criteria

- Person with BMI >30 with waist circumference \geq 88cms in women and \geq 102cms in men
- Those aged < 75 years of age
- Patient has diabetes mellitus
- Already in the care of the North West diabetes service
- Able to provide informed consent
- Not pregnant or breastfeeding

Exclusion Criteria

- Person with diabetes with a BMI > 30 with waist circumference < 88cms in women and <102cms in men
- Person with diabetes with a BMI \leq 30
- Those aged \geq 75 years of age
- Any pregnant or breastfeeding person with diabetes
- Any person with diabetes < 18 years of age
- Any person with a cognitive impairment, an intellectual disability or uncontrolled psychotic illness

Lay Description of Participation

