 - HbA1c
 - Absolute cardiovascular risk
 - Psychometric measures (PHQ-9, depression and SF-36 Quality of Life)
 - Decline in Edmonton Obesity status (Padwal, 2011)
- Rationale - the power is in general a function of the possible distributions under the alternative hypothesis. As the power increases, the chances of a Type II error occurring decrease. We conducted power calculations to calculate the minimum sample size required using a target variance for an estimate to be derived from the sample eventually obtained.
- We assumed a Cohens d of 0.5 and a power of 0.95 based on estimates in the peer-reviewed literature.
- We assumed significance criteria of 0.05, the probability of the data implying an effect at least as large as the observed effect when the null hypothesis is true must be less than 0.05, for the null hypothesis of no effect to be rejected.
- Further, this assumed:
 - A follow-up period of at least 6 months for each participant.
 - Not all participants will be cared for simultaneously – there will be multiple intakes e.g. as people exit the program enrol new participants and controls.

Analysis TSRAC Q12

- Data will be exported from DiaBASE (Clinical software program) and entered into Excel (Microsoft) for data cleaning, then imported into Stata 12 and SPSS for analysis.
- Analysis will be performed using SPSS and Stata.
- Descriptive statistics will first be calculated to investigate the proportions of categorical variables and the distribution of continuous variables.
- Pearson's chi-square test or Fisher's exact tests will be utilized for investigation of associations between categorical variables, while independent t-tests will be used to investigate differences in continuous data between the control and intervention groups.
- For dichotomous outcomes logistic regression will be performed.
- For continuous outcome data analysis of covariance will be performed to test the effects of predictor variables.
- Adjusted relative risks (aRR) of metabolic and psychometric outcomes will be calculated for the control vs. intervention groups (with 95% confidence intervals) using a Poisson regression model with robust error variance.
- The regression models will include adjustment for age, pre-existing diabetes, socio-economic status and Asian or indigenous ethnicity.

Please provide additional justification on for the effect size with references.

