- Informed Consent will be gained by the Research Assistant/ Case Manager in written form
- Participant information will be forward to research team immediately and patient booked into next available AMOS Clinic
- As outlined previously, participation is voluntary. Prior to entry into the study potential participants will be informed of their ability to withdraw at any time, without giving a reason should they wish – the intervention and resources being tested in the study will no longer be made available to withdrawn participants. Withdrawn participants will re-enter the normal Adult Diabetes Clinic.
- There will be no payments made to participants involved in the study

Confidentiality and Privacy

Participant names, their details and data will be kept on a password protected database and will only be linked to a study identification number for this research. Patient information will initially be entered into DiaBASE (a clinical software program that is password protected) on computers that are also password protected. On transportation of data from DiaBASE to excel format only THCI numbers will be included initially – to track any missing data initially – this will then be removed at the study identification number allocated.

At this point there is no patient identifiers. All data will be entered into a computer that is password protected, stored in a locked office of the investigator and maintained for a minimum of 3 years after completion of the study.

Safety Considerations

Expected Benefits to the Wider Community

- The development of an evidenced based tiered model for individualised interdisciplinary care to support obesity management and reduce comorbidity risk.
- Improved patient outcomes which in turn reduce health costs to the community
- Improve best practice in the management of obesity
- Will provide information to support change in service delivery and policy development
- Assessment of process and impact outcomes to substantiate and drive clinical and policy change supportive of a multidisciplinary systematic approach for patients living with obesity.
- The development of a model of care that supports the self and medical management of obesity; taking into account the experience and the context for the person as well as their physical measurements and indicators.
- The development of a framework for improved obesity management for rural Tasmanians with diabetes and obesity.

Expected Benefits to Participants

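### The comparator is a waitlist for AMOS in one place and usual care elsewhere, the consent section books patients into AMOS without regard to arm, and no end of the wait is stated

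*Protocol*

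**What the plan says.** **Waitlist.** The first bullet of Study Design describes a "Parallel randomised waitlist control trial conducted in the Diabetes Centre of the THO-North West; individuals wait listed for the obesity clinic", and says that these people become the control group.

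**Usual care.** The Summary has no waitlist: "The project will recruit 212 patients with diabetes and randomise them to active intervention or usual care". Rationale for Study Design says: "The control group will be seen in the usual diabetes clinic with no particular focus on obesity management". The table of differences between the arms starts the control pathway in the Diabetes Clinic and the intervention pathway in the AMOS Clinic. Management of Cross Contamination adds alternate clinic days, a different diabetes educator, and an endocrinologist for the controls who is not involved in AMOS. The section on orlistat and bariatric surgery states that controls receive usual care and are not offered orlistat. The Lay Description of Participation places them in the normal adult clinic.

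**Booking.** Under Seeking Consent, once written consent is given: "Participant information will be forward to research team immediately and patient booked into next available AMOS Clinic". The sentence does not mention arm.

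**Follow-up.** Outcomes sets both primary outcomes (HbA1c and body weight) as intervention against control, at visits up to 24 months and at 6 and 12 months post intervention. Study Intervention invites both arms to continue after month 24 and says that "ongoing data will be collected following intervention period at 6 and 12 months post intervention", in order to judge sustainability.

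**The concern.** A person wait-listed for a clinic is ordinarily expected to enter it. A usual-care control is not. The protocol uses both descriptions and gives no date on which the wait ends, no bar on entry before a named visit, and no rule for data collected after entry. The booking sentence adds to the difficulty, because followed literally it sends a consented control to AMOS at the outset.

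Two planned comparisons depend on the answer. Entry before month 24 would shrink the contrast on both primary outcomes. Entry at month 24 would leave the 24-month comparison intact, but would turn the post-intervention comparison into people who have finished AMOS against people now in it. A null or reversed difference there would say little about whether the benefit lasts.

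This is protocol content. What the control arm receives, and until when, defines the comparison and is not a detail for an analysis plan.

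**Working it through.** **1. Effect of each possible end of the wait.** The post-intervention visits follow a programme of up to 24 months, so the last falls at up to 24 + 12 = 36 months from baseline.

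| When controls could enter AMOS | Comparisons to month 24 | 6 and 12 months post intervention |
|---|---|---|
| At consent (booking line taken literally) | No contrast in clinic attended | None |
| Before month 24 | Diluted from entry onwards | Diluted or lost |
| At month 24 | Intact | Former against current AMOS patients |
| After the 12-month post-intervention visit | Intact | Intact |
| Never | Intact | Intact, but waitlist is the wrong word |

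Only the last two rows protect every planned comparison. The usual-care sections fit the last row. The Study Design label suggests one of the rows with entry, without saying which. The booking line fits the first.

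**2. The plan's own sample size.** Inputs from Statistical Analysis, Sample Size: d = 0.5, power 0.95, significance level 0.05, 106 per arm. Sidedness is not stated.

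- Normal approximation, two-sided: n per arm = 2(1.960 + 1.645)² / 0.5² = 2 × 12.996 / 0.25 = 103.97, so 104. The t-based figure is 105.
- One-sided gives 87 to 88, so the two-sided version is the one that matches.
- Power at 106 per arm: Φ(0.5 × √(106/2) − 1.960) = Φ(3.640 − 1.960) = Φ(1.680) = 0.954. The t-based value is 0.952.

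The stated 106 reproduces. It makes no allowance for controls receiving AMOS.

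**3. Illustration of dilution.** Let c be the share of controls who receive AMOS before the outcome visit, and assume each gains the full effect. Then d = 0.5 × (1 − c). The protocol gives no value for c, so the values below are assumptions.

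| c | d | Power at 106 per arm (normal) | Power (t-based) |
|---|---|---|---|
| 0% | 0.500 | 0.954 | 0.952 |
| 10% | 0.450 | 0.906 | 0.903 |
| 25% | 0.375 | 0.779 | 0.776 |
| 50% | 0.250 | 0.444 | 0.441 |

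A partial effect in those who cross would make the losses smaller.

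**The case against.** The strongest reply is that the operating sections agree with one another. Rationale for Study Design, the table of arms, Management of Cross Contamination, the orlistat section and the Lay Description all keep controls out of AMOS, with no end date. The separation measures are real: different days, educator and endocrinologist. A waitlist control commonly receives usual care while waiting, so the two labels can coexist. Read literally, the booking line would leave no trial, so it is probably loose drafting. The consent material around it is written from the intervention side: the telephone script describes AMOS care, and withdrawn participants are said to return to the normal clinic.

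Much of this stands. It makes usual care throughout the likelier intention. It does not close the gap, because separating two clinics that run side by side does not say when a wait-listed patient's turn comes. The promised post-hoc accounting concerns care obtained through other pathways, not planned entry into AMOS. A booking instruction that works only if staff ignore its wording should be corrected.

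Three stronger readings are tempting and are not supported:

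- *Existing controls move into freed places.* The sample-size text says "there will be multiple intakes e.g. as people exit the program enrol new participants and controls". That recruits new people to both arms. It moves no existing control and should not be cited for this point.
- *Controls start AMOS at month 24.* No section offers it. Study Intervention and the recruitment text describe continued routine review at the Diabetes Centre for both arms.
- *The sample size is wrong.* It reproduces. The lower power figures rest on assumed crossover shares.

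**Conclusion.** The point holds as a conflict in how the comparator is defined. One section makes controls people waiting for AMOS, the booking line ignores arm, the remaining sections describe usual care in a separate clinic, and nothing says whether or when the wait ends. It is more than missing detail, because following the booking line as written, or waitlist in its ordinary sense with entry before the last outcome visit, would spoil a planned comparison on the primary outcomes.

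A reader might infer that controls will receive AMOS while still counted as controls. The documents do not say so, and most of them point the other way. The size of any effect is therefore unknown. The fall in power from 0.95 to 0.90, 0.78 or 0.44 illustrates the risk under an assumed 10%, 25% or 50% crossover with full effect in those who cross.

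**What to change.** Reconcile the passages by stating which comparator is meant.

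- **If controls are never offered AMOS during follow-up**, as most sections suggest, delete waitlist from Study Design and describe a usual-care control there.
- **If controls are to be offered AMOS**, state in Study Design that entry comes only after the last between-arm outcome visit, and name that visit. Should entry be at month 24, end the between-arm comparison there and report the 6- and 12-month post-intervention data as description within the AMOS arm only.
- **In either case**, limit the booking sentence under Seeking Consent to the intervention arm.

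The cost is wording. The one real loss arises if controls are offered AMOS at month 24: the between-arm sustainability comparison is then given up.
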